2.2. Protocol Violations

All the following deviations will be summarized on the ITT patient population and may include:

- Inclusion or exclusion criteria not satisfied.
- Deviations related to the IP administration.
- Repeated use of soap or shampoo other than the products provided by AOBiome.

At the discretion of the Sponsor, major protocol violations, as determined by a review of the data prior to unblinding of the study results and the conduct of statistical analyses, may result in the removal of a subject's data from the PP population. The Sponsor or designee will be responsible for producing the final protocol violation file (formatted as a Microsoft Excel file), in collaboration with Veristat and the data monitoring group as applicable; this file will include a description of the protocol violation and clearly identify whether or not this violation warrants exclusion from the PP population. This file will be finalized prior to hard database lock.

All protocol violations will be presented in a data listing.

3. GENERAL STATISTICAL METHODS

3.1. Sample Size Justification

A total sample size of 116 randomized subjects, divided into 2 arms (placebo or B244) of 58 subjects each allows for a dropout rate of 10%. It is expected that each strata will have at least 52 subjects with sufficient data needed determine the effect of the IP on blood pressure.

With the planned number 52 subjects per arm, the study is powered 80%, to detect a treatment effect = 5.8 (mean change in systolic blood pressure from baseline), standard deviation (SD) = 10.5 (higher SD than was observed in Phase 1b/2a), with alpha = 0.05, using a 2-sample t-test.

Based on the above sample size, the study is powered 90% to detect the treatment effect of 5.8 (mean change in systolic blood pressure from baseline) and SD = 9, using a 2-sample t-test, that was observed in the Phase 1b/2a study.

In the planned analyses, mixed models will be used to account for the correlation of the assessments over time and provide a more robust analysis of the endpoint.

3.2. General Methods

The analyses will be conducted on all participant data when the trial ends. Data will be presented by treatment arm and overall except where noted. Listings will be sorted by treatment, strata, and subject.

Analysis of the change from baseline in systolic and diastolic blood pressure will be performed using a both mixed-effects model repeated measures (MMRM) and an analysis of covariance (ANCOVA). Least squares (LS) means, confidence interval (CI) on the means, and p-values from the model will be presented. In addition, descriptive statistics on the actual values and the change from baseline will be presented for the 4-spray B244 arm, the 8-spray B244 arm, and the placebo arm.

Categorical variables will be summarized by frequency distributions (number and percentages of subjects) and continuous variables will be summarized by descriptive statistics (mean, SD, etc).

Adverse events will be summarized by treatment using the Medical Dictionary for Regulatory Activities (MedDRA) system organ class (SOC) and preferred term. Separate tabulations will be produced for all treatment-emergent AEs (TEAEs), treatment-related AEs (those considered by the Investigator as at least possibly drug-related), and AEs with Grade 3 or higher severity. By-subject listings will be provided for any deaths, SAEs, and AEs leading to discontinuation.

Descriptive statistics for each treatment arm will be provided for clinical laboratory values (eg, serum chemistry) and vital signs data, presented as both actual values and changes from baseline relative to each on-study evaluation. Out of range clinical laboratory values will be listed.

All data will be provided in by-subject listings.

All data listings that contain an evaluation date will contain a relative study day (Rel Day). Pre-treatment and on-treatment study days are numbered relative to the day of the first dose of study medication which is designated as Day 1. The preceding day is Day -1, the day before that is Day -2, etc.

All output will be incorporated into Microsoft Word or Excel files, or Adobe Acrobat PDF files, sorted and labeled according to the International Conference on Harmonisation (ICH) recommendations, and formatted to the appropriate page size(s).

Tabulations will be produced for appropriate demographic, baseline, efficacy, and safety parameters. For categorical variables, summary tabulations of the number and percentage of subjects within each category (with a category for missing data) of the parameter will be presented. For continuous variables, the number of subjects, mean, median, SD, minimum, and maximum values will be presented.

Formal statistical hypothesis testing will be performed on the primary and secondary efficacy endpoints with all tests conducted at the 2-sided, 0.05 level of significance. Comparisons of baseline characteristics will be performed in order to assess comparability of the treatment arms. Summary statistics will be presented, as well as 2-sided 95% CIs on selected parameters, as described in the sections below. P-values will be rounded to 4 decimal places. P-values that round to 0.0000 will be presented as <0.0001 and p-values that round to 1.00 will be presented as >0.9999.

3.3. Computing Environment

All descriptive statistical analyses will be performed using SAS statistical software v9.3 unless otherwise noted. Medical history and AEs will be coded using MedDRA v19.0. Concomitant medications will be coded using the World Health Organization (WHO) Drug Dictionary March 2016.

3.4. Baseline Definitions

For all analyses, baseline will be defined as the most recent measurement prior to the first administration of study drug. Unless otherwise noted below, measurements collected on Day 1A meet this criteria.

3.5. Methods of Pooling Data

Data will be pooled by site for all analyses. With the exception of disposition and baseline tabulations, summary data will be pooled for subjects who received placebo.

3.6. Adjustments for Covariates

Exploratory analyses will include baseline covariates which may impact the response to treatment and will include race (Black/African-American vs Non-Black/African-American), body mass index (BMI) category, and smoking status (current vs other).

3.7. Multiple Comparisons/Multiplicity

Analyses will not be adjusted for multiple endpoints.

3.8. Subpopulations

In-clinic and ambulatory systolic and diastolic blood pressure results will be reported separately for Black/ African-American subjects, pre-hypertensive and Stage 1 hypertensive subjects, age, and sex (male/female). In addition, blood pressure results may be analyzed according to dipper/nondipper ambulatory blood pressure at screening. Nondippers are defined as subjects who have <%10 decrease in nighttime systolic blood pressure compared to daytime systolic blood pressure.

3.9. Withdrawals, Dropouts, Loss to Follow-up

Subjects who drop out after enrollment but prior to randomization will be replaced.

3.10. Missing, Unused, and Spurious Data

In general, there will be no substitutions made to accommodate missing data points. All data recorded on the eCRF will be included in data listings that will accompany the CSR.

When tabulating AE data, partial dates will be handled as follows. If the day of the month is missing, the onset day will be set to the first day of the month unless it is the same month and year as study treatment. In this case, in order to conservatively report the event as treatment-emergent, the onset date will be assumed to be the date of treatment. If the onset day and month are both missing, the day and month will be assumed to be January 1, unless the event occurred in the same year as the study treatment. In this case, the event onset will be coded to the day of treatment in order to conservatively report the event as treatment-emergent. A missing onset date will be coded as the day of treatment.

In all cases, the resulting date will be compared to the AE end date, if present. If the imputed start date is later than the AE end date, then the start date will be set equal to the end date. The imputed start date is used only for determining treatment emergence; data listings will present the partial date as recorded on the eCRF.

For the primary and secondary efficacy endpoints, the primary analysis will be based on the MMRM method, which makes use of fully and partially observed data sequences from individual patients by estimating the covariance between data from different time points. Treatment group means are adjusted to reflect both the actually observed data and the projected outcomes from the patients with missing data.

3.11. Visit Windows

It is expected that all visits should occur according to the protocol schedule. All data will be tabulated per the evaluation visit as recorded on the CRF even if the assessment is outside of the protocol-specified visit window.

3.12. Interim Analyses

No interim analyses are planned for this study.

4. STUDY ANALYSES

4.1. Subject Disposition

A tabulation of the disposition of subjects will be presented by dose assignment and overall. The number enrolled, the number randomized, the number treated in each arm, the number in each strata, and the reasons for study discontinuation will be reported. Summaries of the number in each analysis set will be summarized. Entry criteria and protocol deviations will be listed. Screen failures will be listed.

A by-subject data listing of study completion information including the reason for premature study withdrawal, if applicable, will be presented.

4.2. Demographics and Baseline Characteristics

Demographic and baseline characteristic data summarization will be performed in order to descriptively assess the comparability of strata and treatments. Summaries will be performed on the ITT and PP populations. Data to be tabulated will include age, sex, race, ethnicity, BMI, and smoking history as well as baseline characteristics related to medical history. BMI and age will be analyzed as a continuous variable using descriptive statistics (number of subjects, mean, SD, median, minimum, and maximum). Sex, race, ethnicity, BMI category ($<30 \text{ kg/m}^2$, $\geq 30 \text{ kg/m}^2$), smoking status, and age category (<60 years, ≥ 60 years) will be summarized by frequency (count and percent). Selected baseline variables will be compared to assess the balance of characteristics across the treatment groups. Age and BMI will be compared using ANCOVA and sex, race, and smoking history will be compared using a Cochran-Mantel Haenszel test.

Demography, general and targeted medical history, and smoking history will be presented in data listings.

4.3. Efficacy Evaluation

The primary endpoint in this trial is the decrease in in-clinic systolic blood pressure from Baseline (Day 1A) through Day 28. Durability of the blood pressure change will be evaluated at Day 42, when subjects have discontinued use of IP for at least 14 days.

All evaluations described below will be applied to both systolic and diastolic blood pressure.

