#### **11.6.8 Study Visit 4R-Repeat ABPM**

If the ABPM technical acceptance criteria are not met during the Study Day 4B reading, the ABPM session may be repeated.

Repeat monitoring may be scheduled up to 48 hours after the failed monitoring.

This visit should occur between the hours of 8am +/- 2 hrs

- provide 24 hr ABPM device to the patient
- train the patient on the use of the machine and provide instruction

The patient will come back on Day 2 to remove ABPM machine and check on the readings to make sure the equipment performed as expected.

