### **12.3.3 ABPM test**

The ABPM device will be placed on subject's arm during the clinic visit and recording device will obtain 24-hour blood pressure and heart rate measurements. The ABPM device and cuff may only be removed at the office, after a final manual reading is performed using the ABPM device. The ABPM device will be automatically programmed to inflate every 20 minutes throughout the recording period. The duration of the ABPM test is 24 hrs.

ABPM data will then be transmitted via modem to the Core Lab. Based on pre-established criteria, the ABPM will be reviewed by the Core Lab to determine if it was a technically successful monitoring. If technically unsuccessful, the monitoring may be repeated.

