5. If subject undergoes ABPM procedures and equipment fails, subject will be scheduled for another ABPM session within 48 hours for Visit 1R or 4R.
6. Subjects will be asked to apply the IP twice daily as per their randomization. First IP application will happen in the office under medical supervision.
7. In the event that subject fails the ABPM test on Visit 4B and needs to repeat it, subject should continue applying the IP through Visit 4R. Investigational product and soap/shampoo should be returned to the site on Visit 4R. Every effort should be made by the site to schedule Visit 4R as close to Visit 4B as possible.
8. Weight of an IP kit will be obtained at the at the 1B visit. Weight of an individual bottle that is currently in use will be obtained at each visit. Final weight of the kit will be obtained at Week 4B visit, when kit is returned by the patient.
9. Subjects will be counseled on the use of study medication, diary and answer any questions subject may have.
10. Subjects will be counseled on the use of ABPM equipment.
11. Subjects are to be provided soap and shampoo at Baseline visit. However, soap and shampoo is available upon request in the event that subjects run out of their initial supplies.
12. Soap and shampoo should be returned to the Study Coordinator.
13. Subjects will be asked to fill out study diary for the duration of the study (Baseline-Day 28).
14. Skin swabs will be obtained during the office visit and will be frozen in the -80 freezer and will be shipped monthly to Biostorage labs.
15. AEs will be monitored throughout the trial.

Table 2: Study Flow

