5. CHANGES TO PLANNED ANALYSES

The following changes between the study protocol are described below.

Editorial edits have been made in [Section 1.1.1](#) (Introduction), [Section 1.2.1](#) (Synopsis of Study Design), [Section 1.2.2](#) (Randomization Methodology), and [Section 1.2.5](#) (Efficacy Parameters) to clarify the information from the study protocol.

The schedule of events was changed according to an administrative letter from AOBiome dated 08 February 2017. Subjects were instructed to continue use of IP through end of the ABPM monitoring period (Day 29 [Visit 4B] and to weigh the IP after this visit. Subjects who had already completed the Day 29 visit prior to the notification should have used the IP through Day 28 and weighed the product on this visit.

The SD in the sample size was changed from 11 to 10.5 in order to estimate power correctly.

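### SAP 4.3 credits the Day 42 durability reading with at least 14 days off product, but the SAP's own schedule gives 13 days nominally and 9 to 10 at the early window limit

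*SAP*

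**What the plan says.** SAP 4.3 (Efficacy Evaluation) defines the primary endpoint over Baseline to Day 28 and adds that durability is assessed at Day 42, "when subjects have discontinued use of IP for at least 14 days".

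Three other places in the SAP determine how long subjects have been off product by then.

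- Section 5 (Changes to Planned Analyses) reports the letter of 08 February 2017: "Subjects were instructed to continue use of IP through end of the ABPM monitoring period", which it identifies as Day 29, Visit 4B. For those the letter reached too late: "Subjects who had already completed the Day 29 visit prior to the notification should have used the IP through Day 28".
- Section 1.2.4, Table 1 footnote 7, covers a failed Visit 4B recording: "subject should continue applying the IP through Visit 4R". On timing, footnote 5 says "subject will be scheduled for another ABPM session within 48 hours for Visit 1R or 4R".
- Table 1 keeps the Week 6 visit at Day 42 with a window of plus or minus 3 days, and gives Visits 4A and 4B windows of plus or minus 1 day.

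The protocol supplies two more inputs. Section 11.6.8: "Repeat monitoring may be scheduled up to 48 hours after the failed monitoring". Section 12.3.3: "The duration of the ABPM test is 24 hrs". Protocol 9.14.1 treats Day 28 as the end of application, which was the position before the letter.

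**The concern.** SAP version 1.0 is dated 19 June 2017, four months after the letter. Its schedule and Section 5 were updated for the later end of dosing, but the sentence in 4.3 was not. Neither document ties the Week 6 visit to the actual last dose or sets a minimum time off product. SAP 3.11 tabulates each visit as recorded, even outside its window, so the analysis rules do not enforce 14 days either.

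The sentence gives the Day 42 result its meaning. If a difference between arms is still visible at that visit, a study report that follows 4.3 would describe it as lasting two weeks or more without product, when some subjects may have had a shorter break.

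**Working it through.** **Formula.** Days off product = Week 6 visit day minus last day of product use.

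**The SAP's own figure.** 42 − 28 = 14. It is reproduced only with dosing to Day 28 and a visit exactly on Day 42. Even then the window breaks the minimum: 39 − 28 = 11, or 39 − 29 = 10 if Week 4A itself fell one day late.

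**Inputs for the current schedule.**

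- Last product day without a repeat: Day 29 (SAP Section 5), or Day 30 if Visit 4B is at +1 (SAP Table 1).
- Last product day with a repeat: hook-up at most 48 hours after the failed session gives 29 + 2 = Day 31. Removal 24 hours later gives Day 32. If Visit 4B was at +1, removal is on Day 33.
- Week 6 visit: Days 39 to 45 (SAP Table 1).

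| Last product day | Visit Day 39 | Visit Day 42 | Visit Day 45 | Window days giving 14 or more |
|---|---|---|---|---|
| 28 (Day 29 visit completed before notification) | 11 | 14 | 17 | 42 to 45 |
| 29 (current schedule) | 10 | 13 | 16 | 43 to 45 |
| 30 (Visit 4B at +1) | 9 | 12 | 15 | 44 to 45 |
| 31 (repeat, dosing to 4R placement) | 8 | 11 | 14 | 45 only |
| 32 (repeat, dosing to 4R removal) | 7 | 10 | 13 | none |
| 33 (repeat, removal, Visit 4B at +1) | 6 | 9 | 12 | none |

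**Sensitivity to the reading of Day 29.** Suppose the last application was really the evening before Visit 4B. Taking 22:00 on Day 28 (an assumption) and an 08:00 visit on Day 42, the gap is 14 − 14/24 = 13.4 days, still under 14.

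**Full span.** Stacking the windows gives 39 − 33 = 6 days at the short end. At the long end, a subject who stopped at a Week 4A visit one day early and was seen on Day 45 has 45 − 27 = 18 days. Subjects who stop application early would have longer intervals. The protocol synopsis also allows 28 days of application plus or minus 4, which would move the interval either way and is not included above.

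**The case against.** Much can be said for leaving this alone, and several points stand.

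- The nominal error is one day in 14. Day 42 is outside the primary model (SAP 4.3.1), and the main shell (Table 14.2.1A) gives it only actual values and changes, with no modelled difference or p-value. Durability is not a listed objective or efficacy parameter. All of this stands and limits the weight of the point.
- Section 5 openly says that some subjects used product to Day 28 and others to Day 29, and the listings carry last dose and blood pressure dates by relative day. The interval can therefore be recovered. That makes the correction cheap; it does not make the sentence in 4.3 true.
- The window is symmetric, so a subject dosed to Day 29 and seen on Days 43 to 45 does reach 14 to 16 days. A reader might infer that the statement is false for most subjects enrolled after the letter. The documents do not support that: they give no distribution of visit days, and Section 5 divides subjects by whether the Day 29 visit came before notification, not by enrolment date.
- A reader might also take about 7 days as the typical shortfall. It needs a failed recording, a hook-up at the 48-hour limit, dosing continued to removal and a visit three days early. Footnote 7 asks sites to hold Visit 4R as close to Visit 4B as they can. The rate of repeats is not given; the under-5% estimate in Protocol 12.3.4 concerns failure of the final repeat recording.
- The end-of-dosing rule does not depend on treatment arm, so no bias between arms is shown.

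**Conclusion.** The stated minimum is wrong as written. For subjects on the current schedule the interval is 13 days nominally and 9 to 10 at the early window limit. On the Visit 4R path it is about 6 to 8 days at the extreme. Subjects who stopped at Day 28 have 14 days nominally but 10 to 11 at the early limit, so the minimum fails for them too, and the interval is mixed across subjects.

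This rests on reading dosing through a given day as use up to that date, and on visits falling inside their stated windows. For the repeat path it also depends on whether dosing ends at placement or removal, which footnote 7 leaves open because Visit 4R covers both.

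The consequence is confined to how a descriptive Day 42 result is worded. The primary test is unaffected, and nothing here shows that the statement fails for a majority of subjects or favours either arm. It is a minor correction worth making.

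**What to change.** In SAP 4.3, remove the 14-day minimum and describe Day 42 as nominally 13 to 14 days after the last dose, varying by subject. Do not replace it with another fixed range: the stacked windows already span about 6 to 18 days, and early stopping widens that.

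Add one summary row, by arm, of actual days from last dose to the Day 42 reading (n, mean, SD, median, minimum, maximum), and word any durability statement in the study report by that observed interval. The dates are already planned for output: last dose in Listing 16.2.1 and blood pressure date in Listing 16.2.6.1.

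Reconcile the sentence in 4.3 with SAP Section 5, Table 1 footnote 7 and the Week 6 window. No change to dosing or visits is proposed. The cost is one SAP sentence and one table row, with no new data.

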4.3.1. Weekly In-Clinic Blood Pressure

To assess treatment effect, change from baseline in weekly systolic and diastolic blood pressure values will be analyzed using a mixed effect model that includes the change from baseline at Days 7, 14, 21, and 28. Day 42 will not be used in the primary endpoint analysis. The model will include stratification factors of spray number and hypertension and baseline blood pressure as covariates, with treatment group (B244 or placebo) and visit as fixed effects, and subject as a random effect. The model will include the following interaction terms: treatment*visit, strata*visit, treatment*strata, and treatment*strata*visit. Estimates of the adjusted LS mean, difference in LS means, and corresponding 95% CIs will be obtained from the model.

Linear contrasts of the differences between each treatment group (4 doses or 8 doses) and placebo at each visit will be used to compare the results between treatments using LS means between each active treatment group and placebo. Nominal 2-sided p-values and 95% CIs will be reported at Days 7, 14, 21, and 28.

Treatment group comparisons within each strata will be an exploratory analysis.

Mixed models will be implemented using PROC Mixed in SAS, using an unstructured within-subject covariance matrix and denominator degrees of freedom from the Kenward-Roger method. Other covariance matrices (first order autoregressive process [AR(1)], compound symmetry, independent) may be utilized in the event that the unstructured matrix does not converge. In this event, the matrix structure that converges provides the lowest akaike information criterion (AIC) value will be selected.

This modeling will be performed for both systolic and diastolic blood pressure, in both the ITT and PP populations.

In addition to the model results, descriptive statistics will be presented by treatment for actual value and change from baseline at each visit (Days 0, 7, 14, 28, and 42). Tabulations will be performed for both the ITT and PP populations. Statistics will also be presented for the subgroups of African-American/non-African-American, pre-hypertension/Stage 1 hypertension, male/female, and age <60/ 60 subjects in the ITT population. Additionally the mean difference between the active treatment group and the placebo for each category of the subgroup along with the 95% confidence interval and p value will also be presented. In addition, mixed model analyses of change from baseline will be performed separately for the pre-hypertensive and Stage 1 subjects using both ITT and PP populations.

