## **11.6 Description by type of visit**

### **11.6.1 Screening Visit (-14 to -7)**

This visit should occur between the hours of 8am +/- 2 hrs

- informed consent completed and signed
- inclusion and exclusion criteria
- demographic data
- medical/surgical history
- current medications
- smoking status
- physical exam
- body weight
- height measurement
- obtain in clinic blood pressure and heart rate
- 12-lead ECG
- blood for clinical chemistry
- urine pregnancy test (for women of childbearing potential)

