### **12.3.4 ABPM technical success/failure criteria**

The following are the technical acceptance criteria against which subject ABPM data will be evaluated:

- Subject dosing of study medication must occur no earlier than 6:00 AM and no later than 10:00 AM.
- There should be at least one (1) manually initiated ABPM reading after dosing of study medication. If no manual post-dose reading was recorded, START TEST time will equal the 1st valid reading after dosing, provided that the reading occurs between 6:00 AM and 10:00 AM.
- There should be a final manual reading on or after 24 hours of recording. If a manual reading was not recorded, the first recording after 24 hours will be considered the last valid recording of the session.
- There must be at least one (1) valid reading per hour with the following possible exception: no more than three (3) non-consecutive hours with zero (0) valid readings during the recording period and two (2) consecutive hours with zero (0) valid readings during the recording period.

Failure to achieve any one of the above criteria will result in the ABPM being declared a technical failure.

If a subject has a technical failure on their repeat recording at Baseline, those subjects will be excluded from the study. However, if subjects passes their baseline and fails the final repeat recording, data will be included in the Office BP analysis but be excluded from the ABPM analysis. We would estimate that this will occur in less than 5% of patients.

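### The in-clinic blood pressure models adjust for at most one continuous pre-dose value, although Screening clinic BP and a baseline ABPM are also collected: a small, nearly free precision gain is left unused

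*SAP*

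**What the plan says.** The primary in-clinic model (SAP 4.3.1) takes "stratification factors of spray number and hypertension and baseline blood pressure as covariates", with treatment, visit and interactions. SAP 3.4 sets baseline as the latest pre-dose value and adds: "Unless otherwise noted below, measurements collected on Day 1A meet this criteria". SAP 4.3 names Day 1A in the primary endpoint. Under Protocol 12.2 a clinic value is the mean of readings 2 and 3 out of three.

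Two other BP measurements precede the first dose:

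- **Screening.** Protocol 11.6.1 lists "obtain in clinic blood pressure and heart rate".
- **Baseline ABPM.** The device is fitted at Day 1A (Protocol 11.6.2). At Day 1B its removal is listed ahead of treatment allocation and first application (11.6.3). A failed session must be repeated before any other Day 1B activity (11.6.4), and Protocol 12.3.4 adds: "If a subject has a technical failure on their repeat recording at Baseline, those subjects will be excluded from the study".

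Neither is a covariate in SAP 4.3.1, in the supportive ANCOVA (4.3.1.1) or in the exploratory list of race, BMI category and smoking (3.6). The ANCOVA text in 4.3.1.1 names no baseline covariate at all, whereas the footnote of Table 14.2.2A includes the baseline value.

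**The concern.** Clinic BP at a single visit is a noisy measure of a person's usual BP. Further pre-randomisation measurements of the same quantity can absorb residual variance. In a linear model with randomised treatment they do this without changing the treatment difference being estimated and without introducing bias. The data are already planned and required, so leaving them out saves nothing.

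Most is at stake where the numbers are smallest: each dose against pooled placebo, and the separate models for pre-hypertensive and Stage 1 subjects (SAP 4.3.1).

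**Working it through.** **1. The plan's own power.** Inputs from SAP 3.1 and 3.2: "With the planned number 52 subjects per arm, the study is powered 80%, to detect a treatment effect = 5.8"; "standard deviation (SD) = 10.5 (higher SD than was observed in Phase 1b/2a), with alpha = 0.05, using a 2-sample t-test"; "powered 90% to detect the treatment effect of 5.8 (mean change in systolic blood pressure from baseline) and SD = 9"; "all tests conducted at the 2-sided, 0.05 level of significance".

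Standard error = SD × √(2/52), and power follows from 5.8/SE.

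- SD 10.5: SE = 2.059, ratio 2.817, power 80.4% (normal) or 79.7% (t).
- SD 9: SE = 1.765, ratio 3.286, power 90.8% (normal) or 90.2% (t).

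Both stated figures reproduce. They come from an unadjusted t-test, so the choice of covariates does not affect them.

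**2. Upper guide for a second clinic baseline.** Suppose all visits share a correlation r. Residual variance is proportional to 1 − r² with one baseline visit and 1 − 2r²/(1 + r) with two. At r = 0.5 this is 0.750 against 0.667, a cut of 11%. The cut is 8% at r = 0.4 and 17% at r = 0.7. This overstates the gain, because the model already carries hypertension status and eligibility restricts the SBP range.

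**3. Simulation with those features.** Screening SBP is limited to 120-159, hypertension status is set at Screening SBP ≥140 and is already in the model with Day 1A, and SD of change is 9 or 10.5. Two sets of assumptions, neither taken from the documents:

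- *Set A:* visit-to-visit correlation 0.4-0.7; correlation of ABPM with true clinic SBP 0.3-0.7.
- *Set B:* usual SBP with mean 134 and SD 8-14; clinic visit error SD 7.42 or 6.36 (SD of change divided by √2); ABPM error SD 6; with or without a lasting between-person clinic-ambulatory difference of SD 5-10.

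Cut in Day 28 residual variance relative to Day 1A plus hypertension status:

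| Assumptions | + Screening | + Screening and ABPM |
|---|---|---|
| Set A | 2.5-6% | 3.5-10% |
| Set B, lasting difference SD 5-10 | 4-8% | 7-14% |
| Set B, no lasting difference | 4-8% | 13-17% |

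A variance cut v is worth 1/(1 − v) − 1 in sample size: 3.5% gives 1/0.965 = 1.04, or 4% more subjects, and 17% gives 1/0.83 = 1.20, or 20% more. For the average over Days 7-28, Set A gives 8-22% with both covariates. Day 28 is used here because the SAP reports contrasts by visit.

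**4. Power for 5.8 mmHg at SD of change 10.5, Day 28, two-sided 0.05 (t).** SE = residual SD × √(1/n₁ + 1/n₂). Four equal groups (SAP 1.2.2) and pooled placebo (SAP 3.5) make the dose contrast about 52/2 = 26 against 52.

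| Scenario | Residual SD, plan → both added | 52 v 52 | 26 v 52 |
|---|---|---|---|
| A: r 0.4, ABPM 0.3 | 8.52 → 8.37 | 93.0 → 93.8% | 79.9 → 81.3% |
| A: r 0.7, ABPM 0.7 | 9.08 → 8.64 | 89.7 → 92.4% | 74.7 → 78.7% |
| B: usual SD 10, lasting difference SD 10 | 8.98 → 8.59 | 90.3 → 92.6% | 75.6 → 79.2% |
| B: usual SD 10, none | 8.97 → 8.28 | 90.4 → 94.3% | 75.7 → 82.1% |
| B: usual SD 14, none | 9.18 → 8.35 | 89.1 → 93.9% | 73.8 → 81.5% |

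The gains are about 1-5 points overall and 1-8 points for a dose contrast. For the dose contrast, Set B starts from about 74-77%; the 80% start occurs only at the lowest correlation in Set A.

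**The case against.** The strongest reply is that nothing here is defective. The baseline rule, the endpoint and the model agree on Day 1A and are pre-specified. The model already adjusts for baseline BP and hypertension status. At SD 10.5 it reaches about 89-93% power for the main comparison, against a planned 80%. All of that stands, and it makes this an improvement and not a correction.

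Four stronger readings are tempting, and the documents do not support them:

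- *That baseline is one reading.* It is the mean of two readings at one visit (Protocol 12.2).
- *That the other measurements are discarded.* Baseline ABPM is used in its own analyses (SAP 4.3.3). If hypertension status is set from Screening BP, part of that information is already in the model. The documents do not say which visit sets it.
- *That the sample size is wrong or the estimate biased.* The stated power is unadjusted and reproduces.
- *That a 13-17% variance cut is established.* It requires daytime ABPM to track clinic BP with error SD 6 and no lasting clinic-ambulatory difference between people. The documents give no figure for this.

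It is also fair to object that filling a missing covariate runs against Protocol 15.3.9 and the general no-substitution rule in SAP 3.10. That holds unless an exception is written in.

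**Conclusion.** The point holds as an efficiency improvement. Two pre-randomisation BP measurements, available for nearly every subject, are absent from both in-clinic models, and adding them would be valid.

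The size is modest and depends on assumptions: a Day 28 residual variance cut of about 2.5-8% from Screening SBP alone and about 3.5-17% from both. How well ABPM tracks clinic BP decides where in that range the trial falls. The main comparison is comfortably powered either way, so the practical benefit lies mainly in the dose-specific contrasts. The change is worth making because it costs almost nothing. The planned analysis remains valid without it.

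**What to change.** Before unblinding:

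1. In SAP 4.3.1 and 4.3.1.1, add Screening in-clinic SBP and baseline daytime ABPM mean SBP as covariates, with the diastolic counterparts in the DBP models.
2. Keep Day 1A as the value subtracted and as a covariate in 4.3.1. Write it into the ANCOVA text of 4.3.1.1 so that the text agrees with the footnote of Table 14.2.2A.
3. State that a rare missing baseline covariate is filled with its overall mean across arms, so that no ITT subject is lost for that reason. Record this as an exception, for covariates only, to SAP 3.10 and Protocol 15.3.9.
4. State which visit sets hypertension status, and update the model footnotes of the Table 14.2.1 and 14.2.2 shells.

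Cost: two extra parameters per model (more if each is crossed with visit), a few SAP edits and no new data.
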